#### SPONSOR: GW PHARMA LIMITED

# 7 PATIENT ENROLLMENT

Before patients may be entered into the trial, GW requires a copy of the relevant site's institutional review board (IRB) or independent ethics committee (IEC) written approval of the protocol, informed consent form (ICF), and other patient information material. Patients will be considered enrolled in the trial from the time of providing written informed consent. All patients must personally sign and date the consent form prior to any procedures being performed (refer to Section 9.2.1 and Section 15.2).

# 7.1 Treatment Assignment

At the start of Visit 1, enrolled patients will be allocated a unique patient number in a sequential order by trial site. Following randomization, GW will provide all IMP in a packed and labeled state, and the IRT will identify the pack number to be dispensed to the patient at each relevant visit according to the treatment arm assigned in the randomization schedule.

# 7.2 Randomization

The allocation of IMP to treatment number will be done according to a randomization schedule produced by an independent statistician. The treatment allocation schedule will have balanced randomly permuted blocks, stratified by region (US versus non-US) and prior cannabis use defined as any pattern of recreational or medicinal use, which would typically exclude isolated, unintentional, or passive exposures. Investigator judgment should be applied during the clinical interview to determine if there is a history of intentional, repeated use of cannabis or cannabinoid products. The randomization schedule will be held centrally on the IRT and not divulged to any other person involved in the trial until the database has been locked and unblinding authorized by the relevant GW personnel. For access to blinded treatment assignment, see Section 8.5. Patients who withdraw from the trial will not be replaced.

#### SPONSOR: GW PHARMA LIMITED

# 8 TREATMENT PROCEDURES

# 8.1 Investigational Medicinal Product Dosage, Administration, and Schedule

The IMP will be presented as a pump oromucosal spray. Nabiximols oromucosal spray is a mixture of THC and CBD extracts derived from *Cannabis sativa* L. Each of the botanical extracts contains a cannabinoid as the major constituent (i.e., THC or CBD) and minor constituents, including other cannabinoid and noncannabinoid plant components, such as terpenes, sterols, and triglycerides.

The use of placebo in the current trial is deemed necessary to determine the efficacy or safety of the current intervention(s), since the best proven intervention has already been tried/is being given as background treatment and has failed to/does not fully alleviate the patient's symptoms. Placebo to match nabiximols is presented as an oromucosal spray containing excipients, coloring, and flavoring, with no active ingredients.

For details regarding IMP formulations, see Section 5.

# 8.1.1 Dose Administration

For all treatment arms, IMP will be administered by the patient via a pump oromucosal spray. The IMP will be self-administered to the oral mucosa. Patients will receive IMP dosing training from site staff on Visit 2 (Day 1 predose). Patients will be advised to administer IMP at approximately the same time each day in a consistent manner in relation to food consumption. Morning and evening doses should be administered around the same time within 30 minutes after starting a snack or meal. Patients should divide doses greater than 1 spray/day into a morning dose and an evening dose.

Following the titration phase (see Section 8.1.2), IMP will be administered as 1 spray (100  $\mu$ L per spray) with a target interval of approximately 1 minute until the patient's specific optimized dose has been administered. Patients should be advised to direct each spray at a different site on the oromucosal surface, changing the application site for each spray of the IMP, and patients should divide doses greater than 2 sprays/day into a morning dose and an evening dose. If lesions are observed or persistent soreness is reported, the IMP administration must be interrupted until complete resolution occurs. Events of this nature are to be recorded according to the adverse event (AE) procedures (see Section 12).

# 8.1.2 Dose Escalation and Dose Adjustments

After IMP dosing training and IMP dispensing, site staff will provide patients with an example titration schedule and instructions to record IMP dosing information in the patient electronic diary. Patients will initiate IMP treatment as a single spray in the

evening on the first day of the titration phase. Patients will be advised to titrate IMP, to the maximally acceptable dose, balancing efficacy and tolerability, beginning with 1 spray/day, to an optimized dose or to a maximum number of 12 sprays/day over the first 14 days of treatment. During the titration phase, there should be an approximately 15-minute interval between sprays. Patients may temporarily pause or slightly reduce the number of sprays upon the emergence of AEs, the titration may be resumed when the AEs resolve. No further dose adjustments should take place after 14 days unless advised by the investigator. An example titration regimen is presented in Table 8.1.2-1.

Patients should not take more than 12 sprays/day of IMP at any time during the trial. Patients should consult the dosing instructions provided and contact the investigational site when in doubt about changes in the daily dose of IMP at any time during the study.

Table 8.1.2-1	Example Titration Schedule				
Day	Number of Sprays in the Morning	Number of Sprays in the Evening	Total Number of Sprays/Day		
1	0	1	1		
2	1	1	2		
3	1	2	3		
4	2	2	4		
5	3	2	5		
6	3	3	6		
7	4	3	7		
8	4	4	8		
9	5	4	9		
10	5	5	10		
11	6	5	11		
12	6	6	12		
13	6	6	12		
14	6	6	12		

Patients should complete titration within 14 days of their first dose of IMP and should continue at the same dose level achieved at the end of titration (i.e., their daily optimized dose)  $\pm 1$  spray divided into a morning dose and an evening dose for the remainder of the treatment period. This guidance applies unless patients agree with the investigator to lower the dose of IMP to address poor tolerability that emerges during the period of stable dosing. For the first 14 days of administering stable doses of IMP following titration, patients should be instructed to gradually decrease the interval between sprays to a target interval of approximately 1 minute between sprays.

The total daily dose should be administered as a morning dose and an evening dose, which may be composed of a different number of sprays. Patients may take their morning dose spread out during the morning and their evening dose spread out during the evening, with a minimum interval between sprays as specified above (i.e., 15 minutes during the titration phase and a target of approximately 1 minute during the maintenance phase).

#### SPONSOR: GW PHARMA LIMITED

# 8.2 Concomitant Therapy

From Screening (Visit 1) forward, any new treatments taken or any change to ongoing medications during the patient's participation in the trial will be recorded on the appropriate electronic case report form (eCRF) page by the investigator or designee. Similarly, any ongoing physiotherapy as part of the management of spasticity at the time of enrollment will be documented in the eCRF as well as any changes in physiotherapy regimen that occur in the course of the study (e.g., discharge from physiotherapy).

For details about the potential for interactions from initiating IMP with prior medications, refer to the guidance for the investigator and potential drug interactions within the IB.

# 8.2.1 Concomitant Optimized Multiple Sclerosis Antispasticity Medications

As nabiximols is being investigated as therapy in patients with spasticity due to MS, all patients must currently be taking at least 1 optimized oral antispasticity medication. Optimized oral antispasticity medications will include at least baclofen, tizanidine, or dantrolene (monotherapy or combination therapy). Their antispasticity medication must have been stable for at least 30 days prior to Screening (Visit 1) and the medication is expected to remain stable through the duration of the trial. However, despite this optimization, eligible patients do not have adequate relief of their spasticity symptoms, including muscle spasms. Optimization of antispasticity medications is defined as having reached the most efficacious and best tolerated dose according to the relevant local prescribing information. The patient must be willing to maintain the same antispasticity therapy for the duration of the trial.

Benzodiazepine use is allowed if doses and dosing regimen have been stable for at least 30 days prior to Visit 1.

If the patient is currently receiving an MS disease-modifying therapy or dalfampridine or fampridine, it must be at a stable dose for at least 3 months prior to Visit 1 and is expected to remain stable for the duration of the trial.

# 8.3 Prohibited Therapy During Trial Period

The following medications are prohibited for the duration of the trial:

- Cannabis use for medical or recreational purposes or any cannabinoid-based medication within 30 days of Visit 1 and for the duration of the trial
- Botulinum toxin injection for the relief of spasticity within 6 months of Visit 1 and for the duration of the trial
- Antipsychotic medication
- Any benzodiazepines use on an as-needed (PRN) basis

- Drugs that are solely metabolized by UGT1A9 and UGT2B7 (See APPENDIX 4)
- Strong CYP3A4 inhibitors or inducers (e.g., rifampicin, carbamazepine, phenytoin, phenobarbital, St John's Wort)

Any patient taking these medications after Visit 1 must cease IMP and should remain in the trial.

The use of psychotropic medications other than those specified above would be allowed provided the medication is used on a daily basis, has been at a stable dose for at least 30 days or 5 half-lives (whichever is longer) prior to Visit 1 and is expected to remain stable throughout the trial.

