# 6.1 Inclusion Criteria

#### Screening (Visit 1)

For inclusion in the trial, patient must fulfill ALL of the following criteria:

- 1. Male or female aged 18 years or above.
- 2. Willing and able to give informed consent for participation in the trial (see Section 15.2).
- 3. Willing and able (in the investigator's opinion) to comply with all trial requirements. (With the exception of the T25FW test, if the patient is non-ambulatory).
- 4. Has had a diagnosis with any disease subtype of MS, by revised 2017 McDonald criteria, for at least 12 months prior to Visit 1 and is expected to remain stable for the duration of the trial.
- 5. Has had treatment with at least 1 optimized oral antispasticity therapy prior to Visit 1 that must include either oral baclofen or oral tizanidine (monotherapy or combination therapy).
- 6. Currently receiving optimized treatment with at least 1 oral antispasticity medication (baclofen, tizanidine, or dantrolene) and has been stable for at least 30 days prior to Visit 1. Despite optimization, the patient does not have adequate relief of spasticity signs and symptoms, including muscle spasms. Optimization of antispasticity medications is defined as having reached the most efficacious and best tolerated dose according to the relevant local prescribing information. The patient must be willing to maintain the same antispasticity medication and not plan to initiate a new course of physiotherapy for the duration of the trial.
- 7. If currently receiving an MS disease-modifying therapy, it must be at a stable dose for at least 3 months prior to Visit 1 and is expected to remain stable for the duration of the trial.
- 8. If currently receiving dalfampridine or fampridine, it must be at a stable dose for at least 3 months prior to Visit 1 and is expected to remain stable for the duration of the trial.
- 9. Willing to allow the responsible authorities to be notified of participation in the trial, if mandated by local law.
- 10. Willing to allow his or her primary care practitioner (if he or she has one) and/or treating neurologist (if he or she has one) to be notified of participation in the trial, if the primary care practitioner/treating neurologist is different than the investigator.

Additional Inclusion Criteria at Randomization (Visit 2)

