- 21. Has any abnormalities identified following a physical examination, clinical laboratory, serology, or other applicable screen procedures that, in the opinion of the investigator, would jeopardize the safety of the patient or the conduct of the study if he or she took part in the trial.
- 22. Has any history of suicidal behavior in the 5 years prior to Visit 1 or a suicidal ideation score of 3, 4, or 5 on the Columbia Suicide Severity Rating Scale (C-SSRS) in the month prior to Visit 1.
- 23. Has a history of severe psychiatric disorder that may be exacerbated by the use of a cannabinoid-containing product.
- 24. Has donated blood during the 3 months prior to Visit 1 and is unwilling to abstain from donation of blood during the trial.
- 25. Has been previously randomized into this trial.
- 26. Has any known or suspected history of alcohol or substance use disorder within 1 year prior to Visit 1. Patients with nicotine use disorder are allowed to enroll.
- 27. Currently using an illicit drug or current nonprescribed use of any prescription drug. A positive drug test at Visits 1 or 2 for a prescribed medication is not exclusionary at the investigator's discretion. A positive drug test at Visit 1 or predose at Visit 2 for illicit drugs may be repeated locally at the investigator's discretion.
- 28. Has any planned clinical interventions or intends to change any or all medications that may have an effect on spasticity or MS during the trial.
- 29. Currently taking drugs that are solely metabolized by UGT1A9 and UGT2B7 (see APPENDIX 4).
- 30. Currently taking strong CYP3A4 inducers (e.g., rifampicin, carbamazepine, phenytoin, phenobarbital, St John's Wort).
- 31. There is an expectation that the participant will require a new course of treatment with strong CYP3A4 inhibitors during the study duration (e.g., participant with recurrent fungal infections requiring intermittent treatment with itraconazole).

32. Patients who receive a positive coronavirus disease 2019 (COVID-19) antigen test result, potentially suggesting infective status, before randomization may be screen failed, at the discretion of the investigator.

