# 9.2.6 Concomitant Medication

Details of all current medications will be recorded. Any changes in concomitant medication during the trial must be recorded on the eCRF at trial visits. Patients should stop taking any prohibited therapy prior to Screening (Visit 1), as defined in Section 8.3.

Please note: Any vaccination related to COVID-19, that was received within the 12 months prior to Screening should be recorded as a concomitant medication. The information recorded should include the vaccine manufacturer and the dates of administration; differing start and end dates denoting two doses being received, if applicable.

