#### SPONSOR: GW PHARMA LIMITED

# 10 WITHDRAWAL

In accordance with the Declaration of Helsinki, the ICH Harmonised Guideline: Integrated Addendum to ICH E6(R1): Guideline for GCP E6(R2), the US FDA regulations relating to GCP and clinical trials, the EU Clinical Trials Directive, the EU GCP Directive, and/or other applicable regulations, a patient has the right to withdraw from the trial at any time and for any reason, with no obligation to provide a reason, and without prejudice to his or her future medical care by the physician or at the institution.

The patient must be withdrawn from the trial if any of the following apply:

- Administrative decision by the investigator, GW, or a regulatory authority
- Withdrawal of patient consent
- Lost to follow-up

The patient must cease IMP and should remain in the trial if any of the following apply:

- Pregnancy
- Protocol deviation that is considered to potentially compromise the safety of the patient
- Suicidal behavior, or suicidal ideation score of 4 or 5 during the treatment period, as evaluated with the C-SSRS
- ALT or AST  $> 3 \times$  ULN with the appearance of fatigue, nausea, vomiting, right upper quadrant pain or tenderness, fever, rash, and/or eosinophilia (> 5%)
- ALT or AST  $> 5 \times ULN$
- ALT or AST > 3 × ULN and (total bilirubin [TBL] > 2 × ULN or international normalized ratio [INR] > 1.5)
- Any prohibited medication after Visit 1

The patient may be required to cease IMP at the discretion of the investigator and should remain in the trial for any of the following reasons:

- Did not meet eligibility criteria
- Patient noncompliance
- AE (including clinically significant laboratory result) that, in the opinion of the investigator, would compromise the continued safe participation of the patient in the trial
- Any evidence of drug abuse or diversion

- Disease progression (defined as a relapse of MS requiring a change in treatment)
- A positive COVID-19 test result after randomization

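### SAP Appendix 6 lists only strong CYP3A4 inducers, so the prohibited-medication tables cannot count the strong inhibitors that the plan also prohibits

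*Protocol*

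**What the plan says.** **Prohibition.** Protocol Section 8.3 bans "Strong CYP3A4 inhibitors or inducers" throughout the trial and states the consequence: "Any patient taking these medications after Visit 1 must cease IMP and should remain in the trial". Section 10 repeats the stop through a general entry, "Any prohibited medication after Visit 1", which names no drug class.

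**Flagging and tables.** SAP Section 12.3.2 sets out seven prohibited categories. One combines strong CYP3A4 inducers and inhibitors and refers to Appendix 6. The flag is set by checking each recorded medication against Appendices 5, 6 and 7, which are presented as the complete pre-specified list. Section 12.3.2.3 then tabulates flagged use by category and drug name, once for prior and once for concomitant medication.

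**Deviations.** SAP Table 12.4-2, item 29, counts use of either an inducer or an inhibitor as a major important deviation.

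**After early termination.** Addendum Table 7-1 keeps Section 12.3.2 except for post-treatment medication summaries. It keeps Section 12.4 except for summaries of major deviations.

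**Eligibility.** Exclusion 30 covers a patient "Currently taking strong CYP3A4 inducers". For inhibitors, exclusion 31 applies where "There is an expectation that the participant will require a new course of treatment with strong CYP3A4 inhibitors during the study duration", and its example is a "participant with recurrent fungal infections requiring intermittent treatment with itraconazole".

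**The concern.** The SAP defines a category of two drug classes and supplies a search list for one of them. A zero for inhibitors in the resulting tables would look like a finding of no use, when inhibitors had never been searched for. A patient recorded under item 29 for inhibitor use could appear in the deviation output and be missing from the prohibited-medication tables of the same report.

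There is a related mismatch in the protocol. The eligibility criteria treat the two classes differently (current use for inducers, an expected new course for inhibitors), while Section 8.3 treats them alike.

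**Working it through.** There is no plan figure to reproduce. The check is a count of the list and a comparison of texts.

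**1. What Appendix 6 contains.**

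| Drug | ATC codes |
|---|---|
| Rifampicin (including rifamycin) | 10 |
| Carbamazepine | 1 |
| Phenytoin | 4 |
| Phenobarbital | 2 |
| St John's Wort | 1 |
| **Total, 5 drugs** | **10 + 1 + 4 + 2 + 1 = 18** |

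Exclusion 30 gives these same five drugs as its examples of inducers, and the appendix title refers to inducers only. Inhibitors listed: 0.

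**2. Whether another list fills the gap.** Appendix 5 covers drugs metabolized solely by UGT1A9 or UGT2B7. Appendix 7 covers cannabinoids, botulinum toxin, antipsychotics and benzodiazepines. Neither has a CYP3A4 inhibitor category. Itraconazole appears in 0 of the 3 lists.

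**3. A likely source.** Section 8.3 prohibits both classes, but its five bracketed examples are the inducers of exclusion 30. SAP Section 12.3.2 repeats those examples, and Appendix 6 codes them. This is an inference, but it would explain how inhibitors dropped out.

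**4. Which outputs are affected.** Two tables, prohibited prior and prohibited concomitant medication, in one category each. The addendum retains both.

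**5. Where inhibitor use would still be visible.**
- The listing of all medications (SAP Section 12.3.2).
- By drug name, in the non-MS medication tables (Section 12.3.2.1).
- If recorded as a deviation, in the deviation listing and in the all-deviation summary under the prohibited co-medication category (Section 12.4). The addendum drops only the major-deviation summaries.

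**6. Protocol texts side by side.**

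| Use of a strong CYP3A4 drug | Section 6.2 | Section 8.3 |
|---|---|---|
| Current inducer | Excluded (30) | Prohibited |
| Expected new inhibitor course | Excluded (31) | Prohibited |
| Ongoing inhibitor, no new course expected | Not named | Prohibited |

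The third row is the mismatch. Two other provisions bear on it. Section 9.2.6 says "Patients should stop taking any prohibited therapy prior to Screening (Visit 1), as defined in Section 8.3". Inclusion 3 requires the patient to be willing and able, in the investigator's opinion, "to comply with all trial requirements".

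**The case against.** **On the SAP.** The omission is small. Inhibitor use is not lost from the report, since the routes in step 5 remain. The working definitions of important deviations sit in a separate guidance document that is not available here and may hold an inhibitor list. Nothing shows that any patient took a strong inhibitor, so the tables might not change. All of this stands and limits the severity. It does not repair the flagging rule, because Section 12.3.2 ties the flag to the three appendices and to nothing else.

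**On the protocol.** A reader might infer that the protocol admits patients on stable inhibitor therapy. The documents do not support that. No section says such use is allowed, and where stable use is acceptable (benzodiazepines, disease-modifying therapy, dalfampridine or fampridine, other psychotropics) the protocol says so. A patient who follows Section 9.2.6 stops the drug before Visit 1. A patient who will not stop has difficulty meeting inclusion 3. What remains is narrower: Section 9.2.6 is phrased as a recommendation and gives no inhibitor washout, inclusion 3 rests on investigator opinion, and the restriction to new courses in exclusion 31 suggests a distinction that Section 8.3 does not make.

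A reader might also infer that two sites could follow the text and treat the same patient differently. That is not shown: giving IMP alongside a strong inhibitor breaches Section 8.3 by either route. Nor does Section 10 add a second inhibitor rule; it takes its content from Section 8.3.

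**Conclusion.** The SAP gap is clear on the page. Section 12.3.2 sends inhibitors to a list with no inhibitors in it, and two retained tables would carry a category label that their search cannot satisfy. The size is one category in two descriptive tables. The number of patients affected is unknown, because the documents give neither inhibitor use nor the number actually randomized.

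The conclusion assumes that the programmers apply the appendices literally, without a fuller list from elsewhere.

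The protocol point is a secondary wording mismatch, largely mitigated by Section 9.2.6 and inclusion 3. It affects no further patient here, since enrollment was halted by the decision of 9 November 2022.

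A reader might go on to infer bias in the efficacy result or a safety risk. Neither is shown. The primary analysis uses the FAS under a treatment policy strategy, so stopping IMP or recording item 29 does not by itself remove a patient, and the addendum has dropped the per-protocol analysis. Severity: minor.

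**What to change.** **SAP, still worth doing.** Add strong CYP3A4 inhibitors to Appendix 6 by name and ATC code, itraconazole included, and retitle it *Inducers and Inhibitors*. The documents name only itraconazole, so the sponsor must choose the rest of the list. The addendum can carry the change, because its final approval is planned before unblinding. All medications are already to be ATC-coded, so the cost is a code-list update and a rerun of the flag, with no new data. Then check the two tables against item 29 in the deviation listing.

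**Protocol, only if it is reused or enrollment reopens.** Extend exclusion 30 and the matching synopsis bullet so that current use of strong CYP3A4 inhibitors is excluded together with inducers. Section 10 needs no edit because it follows Section 8.3. The cost is a short amendment under Section 16.1.
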